## 1.0 Study Summary

Protocol Information	Description
Study Title	Team Science to Identify and Intervene on Metabolism- and Alcohol-Associated Liver Disease (MetALD)
Study Design	The research design is a mixed-methods randomized controlled trial (RCT) comparing standard and enhanced approaches to screening, brief intervention, and referral to treatment (SBIRT/P) for metabolism- and alcohol-associated liver disease (MetALD). Adults age 21+ with indicated risks for MetALD based on alcohol intake and body mass index (BMI) and who speak Spanish or English are offered free, confidential liver screening with Fibroscan®, a noninvasive, painless ultrasound to measure stiffness and fat in the liver. Procedures include a prescreening survey, in-person screening, a randomization visit, and a ~30-day followup visit. At the end of the randomization visit, participants receive a brief intervention to increase motivation for healthy lifestyle which includes either integrated Fibroscan® results or standard health information. At the end of the followup visit, participants complete exit interviews to obtain qualitative data to supplement quantitative indices of feasibility, acceptability, and small-scale effectiveness.
Primary Objective	The primary aim of the research is to show that SBIRT/P can be optimized by integrating results of noninvasive Fibroscan® liver screening for adults age 21+ from underresourced communities and with behavioral risks for MetALD.
Secondary Objective(s)	Secondary aims are to evaluate the precision of biobehavioral endpoints for alcohol intake, weight-related behaviors, and cardiometabolic health, and to explore plasma biomarkers to indicate likely steatosis and fibrosis, with Fibroscan® as a reference standard.
Research Intervention(s)/Investigational Agent(s)	All participants receive SBIRT/P including a brief intervention to increase motivation for healthy lifestyle, toward the end goal of reducing risk of multiple chronic conditions, including MetALD. In the standard SBIRT/P condition, the brief intervention includes standard health information. In the enhanced SBIRT/P condition, results of noninvasive Fibroscan® liver screening and staging are integrated to optimize intervention benefit.
IND/IDE #	NA
Study Population	Adults 21 years of age or older with concurrent risk factors for MetALD based on alcohol intake and body mass index and who speak Spanish or English.
Sample Size	The target number of participants to be randomized is 40 (20 per condition). An estimated 80 potential participants will complete informed consent prior to in-person screening to confirm eligibility, allowing for screen failures and disinterest.

Study Duration for individual participants	Eligible participants are scheduled for a randomization visit, typically within 5 to 10 business days of in-person screening. Approximately 30 days after the randomization visit, participants return for a followup visit to repeat measures and assess satisfaction with SBIRT/P. The total study duration is typically 45 days or less, with flexibility to accommodate schedules.
Study Specific Abbreviations/ Definitions	Alcohol-associated liver disease (ALD) Alcohol use disorder (AUD) Body mass index (BMI) Metabolic dysfunction-associated steatotic liver disease (MASLD) Metabolism- and alcohol-associated liver disease (MetALD) Motivational Interviewing Treatment Integrity (MITI) Randomized controlled trial (RCT) Screening, brief intervention, and referral to treatment (SBIRT/P) Vibration controlled transient elastography (VCTE)

## 2.0 Objectives

- 2.1 The purpose of this randomized controlled trial (RCT) is to test whether screening, brief intervention, and referral to treatment and prevention (SBIRT/P) is improved by integrating results of noninvasive liver imaging with Fibroscan® for adults age 21+ from underresourced communities who speak English or Spanish and are at risk for metabolism- and alcohol-associated liver disease (MetALD).
- 2.2 This research aims to demonstrate that SBIRT/P is an effective way to identify and intervene for MetALD in underresourced communities. Identifying individuals with alcohol intake and overweight-related risks for MetALD and engaging them in brief intervention to promote healthy lifestyle can reduce risk of multiple chronic diseases, including MetALD. We hypothesize that integrating results of noninvasive liver screening and staging with Fibroscan® liver imaging will enhance the effectiveness of a brief intervention to promote liver and heart health, as compared to a brief intervention with standard health information.

## 3.0 Background

- 3.1 Chronic, steatotic liver disease is a leading cause of death in the United States (US) and worldwide. As alcohol intake and obesity rates remain high and rising, and the population of adults in the US who are at risk for irreversible liver damage and cardiometabolic health problems is substantial, particularly among underresourced communities. Updated nomenclature and criteria provide a standardized, inclusive, and nonstigmatizing framework to identify adults at risk for or with steatotic liver disease. In addition to metabolic dysfunction-associated steatotic liver disease (MASLD) and alcohol-associated liver disease (ALD), a concurrent-etiologic type, metabolism and alcohol-associated liver disease (MetALD), identifies those whose drinking may not have yet progressed to the levels seen for patients with ALD but who have an additional cardiometabolic risk factor for chronic steatotic liver disease.
- 3.2 Observational data show that obesity worsens ALD severity, and any drinking accelerates MASLD. Yet, there is currently no preventative interventions or medical treatments to simultaneously address weight-related behaviors and alcohol use to decrease risk for progressive liver damage from both etiologies in MetALD. Importantly, liver disease from alcohol intake and metabolic etiologies is preventable and treatable only through lifestyle changes. Our preliminary data from patients with alcohol use disorder (AUD) and at-risk for or with ALD demonstrated feasibility and acceptability of a brief motivational intervention to reduce alcohol consumption, delivered in English and Spanish for adults recruited from specialty liver clinics and remotely from the community.
- 3.3 Whereas liver-related deaths due to viral infection have declined sharply in recent years through groundbreaking treatments, mortality rates for liver diseases related to alcohol intake and obesity have risen. If left unaddressed, MetALD mortality rates are projected to double by 2040. Research to develop effective strategies to identify and intervene for MetALD in underresourced communities is essential and has potential to help many people avoid irreversible liver damage. Screening, brief

intervention, and referral to treatment/prevention (SBIRT/P) is an effective way to promote liver health and avoid irreversible damage. Interventions to reduce alcohol intake and weight-related behaviors, such as high-fat diet and sedentary lifestyle, are efficacious when delivered, but as many as 90% of those who need intervention are not being reached. In Latinx communities, lack of societal privilege and language barriers can intensify disparities in access to alcohol services, weight management, and linkage to liver care, with deadly and costly outcomes. SBIRT/P integrated at the point of care is a promising strategy to reach people at risk for MetALD, avoid progressive liver damage, and address socioeconomic barriers in communities experiencing health disparities.

## 4.0 Study Endpoints

- 4.1 Primary endpoints include: (a) proportion screened who have alcohol intake and weight-related risks for MetALD; (b) proportion eligible and invited to participate who agree to noninvasive liver imaging with Fibroscan® and arrive for their scheduled appointment; (c) satisfaction with Fibroscan® liver screening; and (d) acceptability metrics for SBIRT/P overall, including retention rates and satisfaction ratings compared across randomized conditions. Satisfaction with Fibroscan liver screening is assessed with a single-item visual analog scale with 0 indicating low satisfaction and 100 indicating high satisfaction. Satisfaction with SBIRT/P overall is assessed with the Client Satisfaction Questionnaire, provided in an attachment.
- 4.2 Secondary endpoints include: (a) self-reported drinking quantity and frequency (e.g., heavy drinking days, drinks per week, alcohol-free days); (b) phosphatidylethanol (PEth), a direct alcohol metabolite biomarker; (c) self-reported weight-related behaviors (e.g., diet quality, eating dysregulation, food cravings, and physical activity); and (d) weight-related biometrics (e.g., body weight, waist circumference, blood pressure). Descriptions and items for secondary-endpoint measures are provided in an attachment. Measures to describe the sample participating in this research, to account for important covariates, and to facilitate team science are also attached. The battery of measures is streamlined from prior projects to reduce staff time, minimize participant burden, and facilitate remote data collection.
- 4.3 Exploratory endpoints include plasma biomarkers to comprise a preliminary panel to screen for likely steatosis and fibrosis in patients at risk for MetALD, with Fibroscan® as a reference standard. These include plasma biomarkers of microbial translocation, innate immune activation, obesity-related metabolic dysfunction, and liver fibrosis.

## 5.0 Study Intervention/Investigational Agent

- 5.1 In the standard SBIRT/P condition: Information about the participant's alcohol- and weight-related risk factors for MetALD is provided. The information includes comparison of the participant's health metrics with public-health guidelines.
- 5.2 In the enhanced SBIRT/P condition: Results of noninvasive liver imaging and staging via Fibroscan® is integrated into the brief behavioral intervention to enhance motivation for healthy lifestyle behaviors, reduce

risk of multiple chronic diseases including MetALD, and promote overall health and wellness. The information includes interpretation of the participant's Fibroscan® steatosis and liver stiffness measurements based on MetALD diagnostic criteria and published liver-health guidelines.

- 5.3 Randomized conditions include either standard or enhanced health information in the setting of evidence-based, motivational interviewing (MI). A treatment manual has been cultivated over decades of research by this team and multiple prior clinical research protocols including our recent study of brief MI for AUD and ALD. The intervention has the potential to have high impact on the dual etiologies of MetALD, i.e., alcohol consumption and weight-related behaviors.
- 5.4 N/A. IND/IDE are not applicable. The Fibroscan® is a well-established research and clinical screening tool for steatosis and fibrosis. Fibroscan® is the gold standard procedure for obtaining information on liver health and is the primary noninvasive diagnostic screening method used in research and clinical practice prior to an invasive liver biopsy.
- 5.5 Fidelity (adherence) monitoring via Motivational Interviewing Treatment Integrity coding system (MITI Coding Manual 4.1; Moyers, Manual, & Ernst, 2014) will evaluate the degree to which the intervention is delivered by the interventionist(s) as intended with consistency across randomized groups and facilitate supervision of the intervention by a licensed clinical psychologist or other licensed practitioner in Rhode Island.

## 6.0 Procedures Involved

- 6.1 Study procedures described herein do not involve more than minimal risk. The research design is a mixed-methods RCT comparing standard and enhanced approaches to SBIRT/P for MetALD. The research, including all procedures and materials, is implemented in English and Spanish. Any modifications of study procedures described herein will be reviewed and approved by the Brown University IRB. The addition of key personnel will be submitted to the IRB and appended to the IRB record upon administrative review. All personnel will have documented human subjects research training prior to engaging in research activities.
- 6.2 This study builds upon prior research through partnering with Clínica Esperanza/Hope Clinic (CEHC) to address issues of low and inequitable access to alcohol health services and liver specialty services across the care continuum. CEHC is the primary site for recruitment and data collection, and established partnerships with Brown Medicine primary care clinics can supplement to meet enrollment targets. The section on recruitment methods provides information to describe recruitment procedures and participant compensation.
- 6.3 Interested volunteers complete a brief, confidential pre-screening survey to assess eligibility and provide basic demographic information to describe the sample of potential participants reached for screening by these procedures. The pre-screening survey questions to assess eligibility and an accompanying script are provided in an attachment. Responses to the pre-screening survey are recorded via Brown-approved, HIPAA-compliant survey software for the purpose of tracking reasons for ineligibility.

Personally identifiable contact information will be securely stored using HIPAA-compliant software vetted and approved by Brown CIS. After pre-screening in partnering clinics or over the phone, a community health worker (e.g., patient navigator or Navegante) or Brown University staff member approaches the potential participant in the clinic or schedules them for an appointment where procedures and risks are explained in person and supplemented by a bulleted written consent form. The consent section of this protocol describes informed consent procedures, which are always done in person via an interactive conversation and documented in writing.

Interested volunteers who would like to participate in screening, appear potentially eligible, and complete informed consent with written documentation continue with screening that day, or, if necessary, are scheduled for a visit as soon as possible. Eligibility criteria assessed include interviews, weight-related biometrics, and blood tests, including tests for Hepatitis B and C which are common exclusionary preexisting liver diseases in this population. Additional measures include culturally validated assessments of diet and lifestyle behaviors, described in attachments.

- 6.4 Those eligible are scheduled for two appointments: (1) a randomization visit typically completed within 5 to 10 business days of in-person screening, and (2) a followup visit ~30 days later. Attendance at all visits is facilitated by reminders in multimethod formats, including email, text message, phone call, and/or calendar invitations, complying with the participant's preferences. The first visit includes the Fibroscan® liver screening, biobehavioral assessments, interviews, and a brief conversation with our study counselor (~45 minutes to 1 hour) to build motivation for lifestyle change. The followup visit repeats biobehavioral assessments and interviews and includes a brief check-in (~15 minutes) with our study counselor with an exit interview assessing satisfaction with study procedures and barriers to change. The Fibroscan® liver screening is not repeated at followup. For participants who are monolingual Spanish speakers or bilingual and prefer to complete the study in Spanish, all procedures including the brief intervention will be implemented in Spanish by bilingual personnel who are either native Spanish speakers or have documented professional Spanish fluency. The total study duration for individual participants is typically less than 45 days, with some variability to allow for flexibility in scheduling.
- 6.5 Plain language is used to describe what will happen during the Fibroscan® and the procedures for sharing results. During informed consent, visual aids are used to facilitate patients' understanding of the procedures, and a specific pause point is written into the bulleted consent form to solicit questions. Participants are informed that they may or may not receive their liver scan results from their study counselor and that this is decided randomly, like a coin flip. In the enhanced condition, our study counselor receives the Fibroscan® results and shares these with the participant in the context of the brief motivational interviewing intervention. In the standard condition, the same brief motivational interviewing intervention is implemented but includes standard information on lifestyle behaviors and risks without the specific results of the Fibroscan® examination. In both conditions, the Fibroscan® results are reviewed by our study physician, [name], who is a Brown-affiliated faculty member and

experienced hepatologist directing the Chapman Street Hepatology Clinic and is chief of gastroenterology at the Providence VAMC. Fibroscan® results can be reviewed remotely via encrypted, HIPAA-compliant communication and software provided by the manufacturer, Echosens, <https://www.echosens.com/en-us/>. Referrals to primary or specialty care for an evaluation will be facilitated by [name], as appropriate, consistent with best-practice clinical guidelines. There is also an independent medical monitor for this study, [name], PhD, an addiction-scientist and hepatologist with extensive experience in this role. [name] will review individual serious adverse events as well as cumulative progress reports and make recommendations regarding safety and continuation of the study.

- 6.6 Sources of research data include (a) self-reported data collected by trained staff via interviews and questionnaires, (b) self-reported data collected via HIPAA-compliant survey tools that have been vetted and approved by Brown CIS, stored on HIPAA-compliant, cloud-based servers, and monitored by staff with up-to-date human subjects training, (c) biological specimens collected, stored, and transported by trained staff, and processed in our Clinical Laboratory Core (CLC) laboratory at Brown University or at HIPAA-compliant clinical laboratories (d) biometrics (e.g., height, weight, blood pressure, waist circumference) collected by research staff using structured protocols, and (e) transient elastography Fibroscan® to obtain Controlled Attenuation Parameter (CAP)TM score and Liver Stiffness Measurement (LSM) by Vibration Controlled Transient Elastography (VCTETM) implemented by trained operators certified by the manufacturer, Echosens, and monitored on site and remotely by our clinical partners, our CLC staff including a study nurse practitioner, our study physician, and an independent medical monitor.
- 6.7 The primary research site for storage and analysis of biospecimens and other data will be the human laboratory at the Center for Alcohol and Addiction Studies (CAAS) at Brown University, School of Public Health, [name]. The section on data safety monitoring gives more information.
- 6.8 Visits are expected to be completed at CEHC at [name], or through Brown Medicine primary care clinics or similar, though the availability of our laboratory offices at [name], School of Public Health provides additional flexibility in the case of unforeseen interruptions in access to appropriate space and resources to complete the research protocol as described herein.
- 6.9 Fidelity (adherence) monitoring via Motivational Interviewing Treatment Integrity coding system (MITI Coding Manual 4.1; Moyers, Manual, & Ernst, 2014) will evaluate the degree to which the intervention is delivered by the interventionist(s) as intended with consistency across randomized groups. Global ratings include two relational components, i.e., partnership and empathy, rated from 1 to 5, with 5 indicating better adherence. Technical components, i.e., cultivating change talk and softening sustain talk, will also be given global ratings. Finally, behavior counts will be used in the context of supervision to monitor the interventionist skill level and identify any areas for improvement. This process typically includes coding 10-minute segments of a random selection of sessions. Our goal is to exceed that

standard and code 10-minute segments for all 40 sessions for all 40 randomized participants (i.e., one session per participant). Following best practices, two raters will use the MITI coding system to maximize and assess the reliability of the MITI for assessing intervention integrity, including both relational and technical components. Supervision is implemented via audio recordings of interviews, and an option to opt out of audio recording is included on the bulleted consent form.

- 6.10 N/A. There are no plans for a long-term followup.
- 6.11 N/A. The study does not test a Humanitarian Use Device (HUD).

## **7.0 Data and Specimen Banking**

- 7.1 Data and specimens will be banked for future use. Specimens will be stored at Brown's SPH lab until they are used for research purposes or discarded. The specimens will be accessed by primary members of the research team and core lab staff. Future use may involve sending the specimens to clinical and/or research laboratories outside Brown for the purpose of performing further testing, assays, and similar functions.
- 7.2 The data to be stored with each specimen include study ID number, date of collection, and visit number, where applicable. No personal identifying information is stored with study specimens under any circumstances.
- 7.3 The specimens will remain under the control of the researchers and will not be released to outside parties.

## **8.0 Sharing of Results with Subjects**

- 8.1 The conditions for sharing results with subjects and others is described via an interactive informed consent process including a conversation with a trained research team member supplemented by a bulleted consent form. The bulleted consent form includes a section on "Your Liver Results" which describes procedures for random assignment in plain language. Participants who are not randomly selected to receive their results at the randomization visit in the context of the brief intervention can be given these results at the end of their followup visit upon request. These results are prepared in a report that includes information provided in standard medical practice, such as in a health portal report. Participants are free to share these results with their primary care physician together with a copy of our bulleted consent form which provides information about the study procedures and contact information for the researchers. Participants are told, "...our doctor who specializes in liver health reviews your scan results. If the scan shows cause for concern, we will tell you and give you a copy to give to your doctor. If you do not have a doctor, we can help you find one. If our liver doctor thinks you need to go to a specialty liver clinic, we will help you make an appointment."
- 8.2 Trained staff inform potential participants of what will happen if blood tests for Hepatitis B and/or C return positive results. If these tests are positive, the findings will be reported to the Rhode Island Department of Health as required by State law. This information is kept confidential by the Department of Health and is used to track diseases. This information is provided verbally and in writing on the bulleted consent form.

8.3 At the conclusion of this research study, the results will be shared with the clinics and communities who participate. There are opportunities for collaborative dissemination via local, regional, and national presentations, as well as publication in academic journals or other appropriate outlets. Individual names or any other personally identifiable information for participants or those screened for research participation are never included on presentations or publications.

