- All team members complete thorough training on the protocol and procedures consistent with their duties on the project. Team members complete CITI training prior to research engagement as well as EHS biosafety training where indicated.
- Weekly team meetings, or more frequent meetings at some stages of training and data collection, ensure that staff are closely supervised and obtain a high level of proficiency.
- Individuals conducting the Fibroscan® are trained operators certified by Echosens, the manufacturer of our Fibroscan® ultrasound machine. Individual Fibroscan® results are reviewed by a study physician who will instruct the team on appropriate next steps and referrals.

- Sessions with the study counselor are audio-recorded with sections selected at random for review and coded by supervisors to ensure fidelity to the intervention protocol. Interventionists are supervised at a minimum biweekly and typically weekly and are given feedback on adherence to the protocol.

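### Could notices of concerning scans reach the standard arm before follow-up, and does the plan need to count them?

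*Protocol*

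**What the plan says.** The enhanced session interprets the participant's "steatosis and liver stiffness measurements based on MetALD diagnostic criteria and published liver-health guidelines" (Protocol 5.2). The standard session is the same motivational interview but "includes standard information on lifestyle behaviors and risks without the specific results of the Fibroscan® examination" (6.5). The scan comes before follow-up: "The first visit includes the Fibroscan® liver screening, biobehavioral assessments, interviews, and a brief conversation with our study counselor" (6.4), with follow-up about 30 days later.

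Two routes lead from the scan to a standard-arm participant:

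- **On request.** Participants not allocated to receive results in the session "can be given these results at the end of their followup visit upon request" (8.1).
- **For safety.** "In both conditions, the Fibroscan® results are reviewed by our study physician" (6.5), and "Individual Fibroscan® results are reviewed by a study physician who will instruct the team on appropriate next steps and referrals" (25.7). The corresponding promise to participants is "If the scan shows cause for concern, we will tell you and give you a copy to give to your doctor" (8.1), with help in finding a doctor or a specialty clinic. On referral, 6.5 says "Referrals to primary or specialty care for an evaluation will be facilitated by" the study physician, as appropriate.

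Only the first route has a stated time. The SAP regresses drinking outcomes on arm, with age, sex, ethnicity and baseline level as covariates. It names three primary outcomes: the proportion screened who are eligible, the proportion of those who agree to the scan, and satisfaction with the scan after baseline procedures. Protocol 4.1(d) adds retention and overall satisfaction compared between arms.

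**The concern.** A standard-arm participant who is told that the scan is worrying, and is handed a copy, has received part of what defines the enhanced arm. If that happens before follow-up, the drinking contrast probably shrinks, and a null result could be misread as showing that feedback adds nothing. Retention and satisfaction under 4.1(d) are measured over the same window, although the direction of any effect on them cannot be stated.

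The process measures in the plan would not reveal this. Fidelity coding (6.9) rates 10-minute session segments for interviewing skill. The CONSORT diagram (17.1) covers screening and enrolment. Stored scan values do not show who was told, or when. Since 17.1 lists arm-specific fidelity among the purposes of the pilot, a count of early notices looks like a natural omission to repair.

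**Working it through.** **1. Is there a contradiction?** Protocol 6.5 says participants may or may not hear their results from the study counsellor. What it withholds is therefore the result within the counselling session. The same section has the physician review scans in both conditions, with referral where appropriate. The promise in 8.1 belongs to that second channel, so the two sections are compatible.

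**2. Is the timing missing from the plan?** It is missing from the visible text. The 8.1 sentence is a partial extract of what participants are told. The consent form has a section on liver results, and 17.3 refers to detailed manuals and standard operating procedures. None of these is in view, so it cannot be concluded that the timing is unset or that notices go unrecorded.

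**3. How large could dilution be?** The documents give no effect size, power, alpha or rate of concerning scans, so there is no figure of the plan's own to reproduce. The only input from the documents is 20 per arm. The rest is assumed:

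- c = share of the standard arm told before follow-up
- q = fraction (0 to 1) of the enhanced effect that a notice delivers
- one common effect for all participants
- two-sided 5% test, unadjusted two-sample t, no dropout

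Share of the effect remaining = 1 − c·q. Sample-size multiplier for a later trial = 1/(1 − c·q)². With q = 1, the worst case:

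| c | Remaining | Power, true effect 0.5 SD | Power, true effect 0.3 SD | Multiplier |
|---|---|---|---|---|
| 0 | 100% | 34% | 15% | 1.00 |
| 10% (2 of 20) | 90% | 28% | 13% | 1.23 |
| 20% (4 of 20) | 80% | 23% | 12% | 1.56 |
| 40% (8 of 20) | 60% | 15% | 9% | 2.78 |

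With q = 0.5 the remaining shares for c = 10%, 20% and 40% are 95%, 90% and 80%. If notices come only after follow-up, c = 0 and nothing is lost.

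**4. Does dilution change what a null would mean?** The 95% interval for the difference has half-width t(0.975, 38) × √(2/20) = 2.024 × 0.316 = 0.64 SD, and 80% power needs a true effect of about 0.91 SD. An observed difference of zero would therefore be compatible with an effect of 0.5 SD whether or not any notice was given.

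**5. What would a count add?** Suppose 4 of 20 were logged as told. Then c = 20%, but q stays unknown, and the remaining share is 80% to 100% only under a common effect. Those told are by definition people with concerning scans. If feedback works twice as strongly in them as on average, q = 1 leaves 1 − 0.20 × 2 = 60%, outside that range. Stored scan values cannot supply a firm upper limit for c either, because the visible text gives no threshold for cause for concern. As a guide to a later trial the count is loose: the exact 95% interval is 6% to 44% for 4 of 20, and 0% to 17% for 0 of 20.

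**The case for a change.** The best argument for acting is that it costs little. One dated field for 40 people, perhaps in the tracking database of 13.7, and one line of reporting would show how well the arms were separated. Dates are easy to record at the time and hard to recover later. At least one case is also plausible: if each standard-arm scan has an assumed 5% to 20% chance of being concerning, the chance of one or more among 20 is 1 − 0.95²⁰ = 64% to 1 − 0.80²⁰ = 99%.

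Most of this stands as fact. The visible promise has no time limit, no visible measure counts notices, and a concerning scan in the standard arm is likely enough. What does not follow is that the plan is deficient without the count. A concerning scan is not the same as a notice before follow-up, whose timing may be set in the consent form. Referral is not leakage, because it is a component of the programme in both arms (Protocol 1.0), so logging it with the notices would blur the measure. The remaining suggestions are already met: the protocol defines the contrast as results integrated into the session versus standard information, and the SAP proposes no as-treated analysis that would move anyone out of the randomised arm.

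**Conclusion.** No change to the plan follows. The gap is one of detail in the visible text, and filling it brings no inferential gain. The as-randomised comparison remains a valid estimate of the two strategies as delivered, including whatever safety notices each arm receives. The three primary outcomes named in the SAP do not depend on the notices. The between-arm comparison in 4.1(d) falls in the same window but also remains valid as randomised.

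The possible dilution of the drinking contrast ranges from nothing (c = 0) to a loss of 40% (c = 40%, q = 1, common effect), and the documents fix neither input. Over that range power at 0.5 SD falls from 34% to 15%, so a null is inconclusive throughout, and a count would neither correct the estimate nor restore power. Analysts who wish to describe arm separation can report the number of early notices from study records where these exist. That is a descriptive courtesy, and the analysis does not require it. This conclusion takes no position on when notices should be given.
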